8. Has availability of a person (“study partner”) who has frequent and sufficient contact with the participant (at least 5 hours per week of in-person contact), can provide accurate information regarding the participant’s cognitive and functional abilities as well as their health throughout the study, agrees to provide information at site visits that require partner input for COA completion, and signs the necessary consent form. (Note: asymptomatic participants require the study partner at the COA visits only; symptomatic participants require the study partner at each visit).
 - The study partner must have sufficient cognitive capacity to accurately report upon the participant’s behavior, cognitive, and functional abilities in the opinion of the investigator. The study partner should be in sufficiently good general health to have a high likelihood of maintaining the same level of interaction with the participant, and participation in study procedures throughout the study duration.
 - The same study partner should participate throughout the duration of Part 1 of the study. If a change in study partners during Part 1 is necessary, the Medical Monitor must be contacted.

Part 1 (Treatment Period) – Inclusion criteria applicable to those UK, US, or Canadian participants participating in the optional Winterlight Labs Speech Assessment (WLA) only:

1. Has available and willing study partner to administer the WLA.
2. Has WiFi access in their residence or WiFi access in a private area where the testing can take place.
3. US, UK, or Canadian participants and study partners must be proficient in English in the investigator’s opinion.

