APPENDIX 2. CLINICAL OUTCOME ASSESSMENTS – NEUROCOGNITIVE AND FUNCTIONAL TESTS

Clinical Dementia Rating Dementia Staging Instrument PLUS National Alzheimer's Disease Coordinating Center Frontotemporal Lobar Degeneration Behavior and Language Domains (CDR® plus NACC FTLD):

The CDR® plus NACC FTLD assessment is the CDR® plus the Frontotemporal Dementia Behavior and Language Domain scores from the NACC FTLD module. Data for this scale will be captured through completion of the standard CDR and a domain-specific container form labeled Frontotemporal Dementia Behavior and Language Domains (FTD-BLD). The necessary information to rate these domains is obtained through a semi-structured interview of the participant and a reliable informant or collateral source (e.g., a caregiver).

Clinical Dementia Rating Scale (CDR®):

Washington University's CDR is a global assessment instrument that yields global scores (CDR-GS). The sum of boxes (CDR-SB) score is a detailed quantitative general index that provides more information than the CDR-GS in participants with mild dementia (O'Bryant 2010). The CDR characterizes 6 domains of cognitive and functional performance applicable to Alzheimer's disease and related dementias: Memory, Orientation, Judgment and Problem Solving, Community Affairs, Home and Hobbies, and Personal Care. The necessary information to make each rating is obtained through a semi-structured interview of the participant and a reliable informant or collateral source (e.g., a caregiver).

Frontotemporal Dementia Rating Scale (FRS):

The FRS is a 30-item scale designed to assess the frequency of problematic behaviors and difficulties with activities of daily living such as shopping, chores, telephone use, management of finances and medications, meal preparation and eating, self-care and mobility.

Clinical Global Impression of Severity (CGI-S):

The CGI-S is a 7-point Likert scale that is used by a clinician to rate the severity of a participant's disease relative to the clinician's past experience with patients who have the same diagnosis.

Clinical Global Impression of Improvement (CGI-I):

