- In the circumstance that the primary rater is remote, and the subject and back-up rater are on-site, scales can still be administered by the primary rater. The primary rater should call in to the visit to administer the CDR® plus NACC FTLD questions over the phone. The back-up rater should observe the subject while they are answering the questions, and then provide observations of the subject behavior to the primary rater. Missing data from direct observation, which cannot be provided by the primary rater, can be completed by the back-up rater, as long as they are appropriately trained on the scale. Final observational assessments should be made by the primary rater.

2. **Frontotemporal Dementia Rating Scale (FRS)**

- **Recommendation:** As a clinician-administered interview with the study partner, the FRS can be administered in person in the clinic, in home, telephonically, or via video conferencing.
- In the circumstance that the primary rater is remote, and the subject and back-up rater are on-site, scales can still be administered by the primary rater. The primary rater should call in to the visit to administer the FRS questions over the phone. The back-up rater should observe the subject while they are answering the questions, and then provide observations of the subject behavior to the primary rater. Missing data from direct observation, which cannot be provided by the primary rater, can be completed by the back-up rater, as long as they are appropriately trained on the scale. Final observational assessments should be made by the primary rater.

3. **CGI**

- **Recommendation:** A general, unstructured evaluation, discussion with an informant, as well as review of data collected from other scales (if not contraindicated by the protocol or study team instructions) may help ensure CGI raters have adequate information to score. Since the CGI is scored based on the CDR® plus NACC FTLD interview, a separate interview is not required.

4. **Sheehan-STS**

- **Recommendation:** This can be completed via phone. Per [name], a copy of scale should be provided for the subject to view when they are being evaluated.

Please note that some scales requiring subject performance, like drawing or writing, are not validated for remote administration and **may not be administered via telephone** (e.g., Color Trails Test [CTT] and Repeatable Battery for the Assessment of Neuropsychological Status [RBANS]).

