9.3. Frontotemporal Dementia Rating Scale (FRS)

The FRS results will be summarized by visit and question. The question results will be summarized using the frequency count and percentage of participants in each response. The FRS Score, FRS Percentage Score, FRS Logit Score, and FRS Severity Category Score will be summarized for actual values and changes from baseline using descriptive statistics. Mean change from baseline, plus or minus the SD, will also be presented in a plot. Subject level data will be presented in a plot, grouped by cohort.

The FRS Score and FRS Percentage Score endpoints will be assessed using MMRM methodology described in [Section 9](#).

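### Appendix 3 conflicts on who answers the FRS when the primary rater is remote, and the SAP's FRS model would not separate any participant-answered scores

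*Protocol*

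**What the plan says.** Protocol Appendix 3, under the remote assessments, has two bullets for the FRS.

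- The first defines how the scale is given: "As a clinician-administered interview with the study partner, the FRS can be administered in person in the clinic", and also at home, by telephone or by video.
- The second applies "In the circumstance that the primary rater is remote, and the subject and back-up rater are on-site". The primary rater is to phone in and "administer the FRS questions over the phone. The back-up rater should observe the subject while they are answering the questions". The back-up rater then passes on what was observed and, if trained on the scale, may complete what is missing from direct observation. The primary rater makes the final observational assessment. The study partner is not mentioned.

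Appendix 2 describes the FRS as a 30-item scale of behaviours and daily activities and names no informant. Protocol Section 4.1.1, criterion 8, requires a study partner who "can provide accurate information regarding the participant", including function, and who attends every visit with clinical outcome assessments.

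On the analysis, SAP Section 9.3 states: "The FRS Score and FRS Percentage Score endpoints will be assessed using MMRM methodology", referring to Section 9. There the outcome is change from baseline. The model terms are cohort, time point and their interaction, and covariates are ruled out because the sample is small.

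**The concern.** A rating scale analysed as change from baseline needs the same kind of informant throughout. If the baseline comes from the partner and a later rating from the participant, the difference between the two informants is added to the change score and looks like clinical change. The population makes this more than a formality. Protocol Section 1.1.1 describes executive dysfunction, behavioural and personality change and language deficits, and primary progressive aphasia is one of the qualifying diagnoses. The study is open-label with a single treatment, so no control arm would share and cancel such a shift. Cohorts are small: Protocol Section 4.1 allows up to 20 participants with *GRN* mutations and up to 20 with *C9orf72* mutations.

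**Working it through.** The plan gives no figure on this point, so the check is a comparison of texts.

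1. **The two FRS bullets.** The first makes the study partner the person interviewed. In the second, the person answering is, on the ordinary reading of the sentence, the participant. The second bullet also brings in direct observation of the participant, which has no stated place in a partner interview. The two do not fit together.

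2. **Where the wording probably came from.** The bullet for the CDR plus NACC FTLD, just above, is almost identical: "questions over the phone. The back-up rater should observe the subject while they are answering the questions, and then provide observations". It fits there, because Appendix 2 describes that instrument as a "semi-structured interview of the participant and a reliable informant or collateral source". The likely explanation is that the text was reused for a scale with a different informant. That is an inference; the documents do not say so.

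3. **Whether other text settles it.** The general guidance later in Appendix 3 covers two cases.
   - If the partner is remote and the participant is on site, the partner still answers, to the site rater. This is a different situation.
   - If the primary rater is remote, the reader is sent back to the CDR and FRS sections, and so to the bullet in question.

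   The instruction to follow the scale manual is general and does not expressly override a scale-specific instruction. Criterion 8 secures the partner's presence but does not say who answers the FRS.

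4. **Whether the analysis would separate the scores.** SAP Section 9 has no term for mode of administration or informant. Section 9.3 has no exclusion, listing or sensitivity analysis for them, and Section 12 (changes in the planned analysis) does not mention them. Remote administration, with any accommodations made, is to be noted on the scale or in source documents. No data field for it is specified.

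5. **Size.** If k of n FRS ratings in a cohort at a visit have a changed informant, and each is shifted by an average of d points, the raw mean change at that visit moves by k × d / n. With one affected rating in a full *C9orf72* cohort, that is 1 × d / 20 = 0.05d. With fewer participants remaining the fraction is larger. The documents give neither k nor d, so the calculation stops there.

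**The case against.** The strongest reply is that this is a drafting slip and not a change of informant. No sentence says the study partner stops being the FRS respondent, and the first bullet says plainly that the partner is interviewed. The partner must attend visits with clinical outcome assessments and agree to give input. The scale manual must be followed when adapting to telephone. A remote partner still supplies the answers, and the general guidance describes the back-up rater as a source of observations only. A separate manual on these assessments, which is not available here, may say more. The situation is also narrow: a COVID-affected site, a remote primary rater, and the participant and back-up rater on site. Remote administration is to be noted, so affected ratings should be partly traceable.

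Most of this stands. It makes participant-answered ratings less likely and limits how many there could be. It does not remove the conflict, because none of these provisions corrects the bullet and the general guidance points back to it.

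Two stronger readings are tempting. A reader might infer that FRS scores at these visits do come from the participant. The documents support only the conditional: this follows if sites apply the bullet literally. A reader might also try to size the effect by dividing 100 by 30 items, about 3.3 percentage points per item, and multiplying by an assumed number of discordant items and an assumed share of affected visits. The documents give no FRS item scoring, no partner-participant disagreement rate or direction, and no count of affected assessments, so such figures would rest on assumption alone.

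**Conclusion.** The internal conflict in Appendix 3 is real, and the remote-rater bullet is wrong as written for a scale defined as a partner interview. If followed literally, it mixes informants in FRS scores that the SAP pools in one change-from-baseline model. The conclusion assumes that at least some sites used the bullet as worded, and that for those participants the informant differed between baseline and the later visit. Neither can be established from the documents, and the size of any effect cannot be derived. The FRS is one of several exploratory clinical endpoints, both documents rule out formal significance testing, and no primary or secondary endpoint is touched. This is a minor point worth correcting because the correction is nearly free.

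**What to change.** **Protocol Appendix 3, FRS remote-rater bullet.** Replace the text that mirrors the CDR bullet with a statement that the study partner remains the FRS respondent wherever the primary rater is, by phone if the partner is not on site, and that back-up-rater observation of the participant does not enter the FRS score. A rater note would serve if an amendment is not practical.

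**SAP Section 9.3.** Use the scale notes or source documents to identify any FRS assessment already answered by the participant. List these assessments and repeat the FRS MMRM without them as a sensitivity analysis. Keep the main analysis as planned: removing the ratings from it outright is harder to justify when the SAP already cites small cohorts and high attrition.

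**Cost.** One replaced bullet, a small check of source notes and one extra analysis. The notes are required to record remote administration and accommodations, but the respondent is not named as an item to record. Where it cannot be established, the listing should say so.

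Specifying the analysis helps even if the affected visits are already complete.

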6.1. Timing of Study Drug Administration

Pre-dose Study Procedures and Assessments:

- Perform COAs prior to any potentially stressful procedure (e.g., blood collections, lumbar punctures, imaging)
- PE, or limited or symptom-directed examination
- Neurological examination, or limited or symptom-directed examination
- Vital signs and weight, including blood pressure (BP), pulse, body temperature, and respiratory rate
- Triplicate 12-lead ECG
- Obtain blood and urine samples for chemistry, hematology, coagulation, serology, pregnancy testing, and urinalysis.
- Obtain blood samples for ADAs
- Obtain blood samples for PK and PD
- Obtain blood sample for whole genome sequencing (WGS) (Part 1 only)
- Collect CSF samples via lumbar puncture for PK and PD (Part 1 only)
- Perform MRI
- Perform Sheehan Suicidality Tracking Scale (Sheehan-STS)
- Review of concomitant medication(s)

- Record any AEs and SAEs

Dosing Procedures:

- AL001 will be administered to participants per institutional practice ([Section 5.1](#)).

Post-dose Procedures:

- Obtain serum samples for PK
- Triplicate 12-lead ECG
- Vital signs, including BP, pulse, body temperature, and respiratory rate
- Review of concomitant medication(s)
- Record any AEs and SAEs

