In the event that a scheduled assessment is unable to be completed at site, e.g., limited availability/restriction of equipment (e.g., MRI), patient limited time on-site or because a remote visit was completed, the missed assessments may be completed at a future on-site visit as determined and approved by the medical monitor.

The approval of the medical monitor must be obtained prior to completion of these moved assessments.

COVID-19 Reporting

In the event where a study subject is diagnosed with COVID-19 infection, the local health authority recommendations regarding treatment should be followed and the event should be reported as an AE/SAE depending on the severity of infection and diagnosis. Refer to [Section 7](#) of the protocol.

Remote Consent

Where it is allowed by country/site regulations, a remote eConsent will be provided that allows a patient to be remote from the site and participate in the consent process.

Remote Source Document Verification

Remote source document verification will be employed **only** in the following circumstance:

- National law, Regulatory Authorities and IRB/Ethics Committee permit this process and approval is obtained.
- On-site clinical research associate (CRA) visits are not permitted due to continued COVID-19 restrictions.
- There is a need to complete source document verification for the following reasons:
 - Study Data assessment review of critical study milestones (e.g., database lock)
 - Patient safety
 - A significant backlog of data monitoring that could impact data integrity or patient safety.

Prior to commencing remote source document verification, the following documentation must be completed:

- The Site CRA will complete a confidentiality agreement committing to securely destroy any copies of documents received from sites (paper or electronic), nor take any recording during video access.

- Remote source data verification (SDV) will only be completed for subjects who have consented to allow access to their health records remotely.

At Home Study Drug Administration

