In most instances, study drug should be administered at the investigational site. In the event the participant is unable to have study drug administered at the investigational site (i.e., due to participant or site restrictions related to Covid-19) study drug administration for the third and subsequent infusions may be performed “at home” (i.e., at the participant’s home or other suitable location) by a home healthcare provider who has appropriate training and expertise in IV administration. Study drug administration for the first and second infusion must be conducted at the investigational site, at home study drug administration for subsequent infusions may only be performed with Medical Monitor approval.

The following procedures must be performed for each at home study drug administration:

Before study drug administration:

- Home healthcare provider will record vital signs, including systolic and diastolic BP, pulse, body temperature, and respiratory rate (recorded after the participant has been resting for at least 5 minutes in the supine position)
- Home healthcare provider will conduct an assessment^{1,2} to include evaluation of general appearance, skin, EENT, head and neck, extremities, abdomen, and respiratory, cardiovascular, neurological, and musculoskeletal systems
- Home healthcare provider will conduct a review of concomitant medication(s)
- Home healthcare provider will record any AEs (signs and symptoms) which may have occurred since previous visit
- Home healthcare provider will contact the investigative site by phone or video (investigator or designee) to review findings from the assessment, adverse events and concomitant medications
- Home healthcare provider must receive email confirmation from the investigative site to proceed with study drug administration, prior to initiating study drug administration.

During study drug administration:

- Approximately 15 and 45 minutes after initiating study drug administration, monitor vital signs, including systolic and diastolic BP, pulse, body temperature, and respiratory rate²
- Monitor for infusion-related reactions or injection-related reactions³
- Record any AEs (signs and symptoms)

After study drug administration

- Record vital signs, including systolic and diastolic BP, pulse, body temperature, and respiratory rate (recorded within 15 minutes after the end of infusion)
- Monitor for infusion-related reactions or injection-related reactions for at least 90 minutes post-infusion³

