- Conduct an assessment^{1,2} to include evaluation of general appearance, skin, EENT, head and neck, extremities, abdomen, and respiratory, cardiovascular, neurological, and musculoskeletal systems
- Record any AEs (signs and symptoms)

If any AEs are observed during or after study drug administration the home healthcare provider must contact the clinical site by phone or video (investigator or designee) to review findings and to take appropriate action(s), if directed by the investigator (or designee).

If required, the site investigator may also conduct a tele visit prior to, during, or after study drug administration.

¹ The assessment will substitute for the protocol specified physical and neurological examination .

² Abnormalities identified during the assessment should be recorded as an AE and reported to the site in order to be entered in the EDC.

³ Management of infusion-related and/or injection-related reactions is described in Protocol [Section 5.1.2](#).

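### The home-infusion procedure does not name the pre-dose pregnancy test, and the COVID-19 catch-up rule lets that test be moved past the dose

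*Protocol*

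**What the plan says.** The ordinary rule is clear. Protocol section 6.1 includes, among the pre-dose procedures, "Obtain blood and urine samples for chemistry, hematology, coagulation, serology, pregnancy testing, and urinalysis". Table 3 footnote c places the urine pregnancy test before study drug, and the sample-timing footnote attached to the pregnancy row of the schedules (g in Tables 4 and 7, h in Table 5, f in Table 8) says the same. Appendix 3's reduced minimum for on-site visits during the pandemic still includes the test.

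For home dosing, Appendix 3 (At Home Study Drug Administration) states "The following procedures must be performed for each at home study drug administration". The items before the infusion are vital signs, a body-system assessment, a review of concomitant medication, recording of adverse events, a call to the site and an email go-ahead. The call is "to review findings from the assessment, adverse events and concomitant medications". The last step is "Home healthcare provider must receive email confirmation from the investigative site to proceed with study drug administration, prior to initiating study drug administration". Home dosing is open from the third infusion, and "at home study drug administration for subsequent infusions may only be performed with Medical Monitor approval". Footnote 1 limits what the home assessment replaces: "The assessment will substitute for the protocol specified physical and neurological examination".

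For assessments not done on schedule, Appendix 3 says "the missed assessments may be completed at a future on-site visit as determined and approved by the medical monitor", and adds "The approval of the medical monitor must be obtained prior to completion of these moved assessments". The same catch-up permission is footnoted to the procedures header of the visit schedules (m in Tables 4 and 5, j in Table 7, i in Table 8).

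**The concern.** The home procedure is the document a visiting nurse works from, and the safeguard that applies at every on-site infusion does not appear in it. Pregnancy is a listed reason for stopping study drug in both parts (sections 4.3.1.1 and 4.4.1), and section 7.12 requires a participant who becomes pregnant to stop. The scheduled test is how an unrecognised pregnancy would be found before the next infusion.

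Deferral does not repair the omission. A late MRI or rating scale still yields usable data, whereas a late pregnancy test cannot protect a dose already given. Because each dosing visit has its own test, one moved to a later on-site dosing visit simply coincides with the test already due there, and the home dose remains untested.

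**Working it through.** No figure in the plan is in dispute, so the check is a comparison of text followed by a count of exposure.

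**Where the test is required or named**

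| Place | Pregnancy test? |
|---|---|
| Section 6.1, pre-dose procedures | Yes |
| Table 3 footnote c | Yes, before drug |
| Schedules (Tables 4, 5, 7, 8) | Yes, at every dosing visit, collected pre-dose |
| Appendix 3, on-site minimum | Yes |
| Appendix 3, remote-visit list | No |
| Appendix 3, home list before, during and after the dose | No |
| Appendix 3, content of the site call | No |
| Appendix 3, condition on the email go-ahead | No |
| Appendix 3, footnote 1 (what is replaced) | Not mentioned, so not waived |
| Catch-up rule and its schedule footnotes | No exception for pre-dose checks |

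**Whether the existing approvals close the gap**

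- Medical Monitor approval of home dosing: nothing ties it to a test result.
- Medical Monitor approval of a moved assessment: it must precede the late assessment, not the intervening dose.
- Site call and email: the call covers the assessment, adverse events and concomitant medication, and the email carries no test condition.

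The catch-up rule also expressly covers an assessment missed because the visit was remote, so a home visit falls naturally within it.

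**Dosing visits with a scheduled test**

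- Table 4: V1 and V3 to V15 = 14
- Table 5: V16 to V26, leaving out V17A = 11
- Table 7: V27 to V42 = 16
- Table 8: V43 to V51 = 9
- Total: 14 + 11 + 16 + 9 = 50

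Cross-check from study days, at 28-day spacing: Part 1, (673 − 1)/28 + 1 = 25; Part 2, (1373 − 701)/28 + 1 = 25; sum 50.

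**Infusions eligible for home dosing**

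Infusions 1 and 2 (Weeks 1 and 5) must be on site, so eligibility starts at Week 9. Part 1: 25 − 2 = 23. Part 2: 25. Total: 23 + 25 = 48 of 50.

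**Delay if the test is moved to the next dosing visit and that visit is on site**

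- Nominal gap: 28 days.
- With ±7 days at each of the two visits: 28 − 14 = 14 days to 28 + 14 = 42 days.
- Each further consecutive home infusion adds 28 days; for two in a row, the first dose precedes the test by 28 + 28 = 56 days nominally.

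**The case against.** The strongest reply is that the general rule still governs. Section 6.1, Table 3 footnote c and the schedule footnotes are not limited to on-site dosing. Appendix 3 says so explicitly where it replaces a procedure, and it does not replace this one. The home list does not claim to be complete: it also leaves out weight, blood draws and the suicidality scale. On this reading a home dose without the test would already depart from the protocol, and only a cross-reference is missing. That stands as far as it goes, because the test is not waived. It does not dispose of the catch-up rule, which gives a written route for moving any assessment missed because a visit was remote.

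Second, several people stand between the participant and an untested dose: the Medical Monitor, the investigator or designee on the call, and whoever sends the email. Women of childbearing potential must also use contraception (inclusion criterion 3b) and are told to stop drug and report a pregnancy. These lower the chance of harm. But no approval step asks for a test result, and the protocol requires contraception and still tests at every dosing visit, so it does not treat contraception as enough.

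Third, the size is unknown and may be nil. On-site dosing is the default, Part 2 is optional, the SAP (sections 2 and 12) reports high attrition, and the appendix applies only under pandemic restrictions. All of this is right and keeps the point modest. The documents available also describe no specific reproductive hazard of the drug.

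Against reading the omission as deliberate, the home procedure is otherwise stricter than on-site dosing: at least 90 minutes of observation after the infusion against 60, and extra vital signs at about 15 and 45 minutes.

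**Conclusion.** The point holds. The home list, the site call and the email go-ahead do not name the pregnancy test, and the catch-up rule does not prevent it being moved past the dose. An existing safeguard has not been carried into the home procedure; the plan does not positively permit dosing without a test.

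The ceiling is 48 of 50 planned infusions, which assumes a participant who completes both parts and has every eligible infusion at home. It applies only to women of childbearing potential dosed at home under COVID-19 restrictions with Medical Monitor approval, and their number cannot be computed from the documents. The delay of 28 days (14 to 42) assumes that the test is in fact moved to the next dosing visit and that this visit is on site. No endpoint, population or analysis is affected. It is a small patient-safety improvement worth considering, not a flaw in the design.

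**What to change.** 1. Add a urine pregnancy test for women of childbearing potential to the home pre-dose list, and make the site's email go-ahead conditional on a negative result.
2. State in the Appendix 3 catch-up rule, and in schedule footnotes m (Tables 4 and 5), j (Table 7) and i (Table 8), that this test may not be deferred past the dose; if it cannot be done, the dose waits.

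The cost is two sentences with matching footnote edits, one urine strip per home visit for the women concerned, a slightly longer visit and an occasional delayed dose. Section 6.5.9 already keeps urine pregnancy testing out of the central laboratory, though it assigns it to local laboratories, so the sponsor should confirm that the home provider may run the test. A positive result would still need the serum confirmation required by Table 3 footnote c, with the infusion withheld meanwhile.
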